6.0 Procedures Involved*

This study is a prospective, randomized controlled trial comparing the clinical and radiographic outcomes of a collared versus collarless femoral stems of the same design in primary THA. A total of 100 participants undergoing elective, uncemented primary THA for degenerative hip disease will be enrolled.

Participants will be randomized in a 1:1 ratio to receive either a collared femoral stem or a collarless femoral stem. All patients indicated for a cementless primary total hip arthroplasty will be offered enrollment. Once consented, they will be randomized into the collared or collarless stem groups. Study participants will be informed about the risk of randomization due to removing the elements of choice from the clinician, as outlined in the informed consent form.

MOD00024127

Page 6 of 18

Revised: November 12, 2025 IRB Approved

12/18/2025 - 11/3/2026

PROTOCOL TITLE: Comparison of clinical and radiographic results of collared and collarless femoral stems in total hip arthroplasty

The primary endpoint is femoral stem subsidence, measured at postoperative 6week, 6-month, and 1-year clinical visits, which coincide with standard of care routine follow-up. Secondary endpoints include the incidence of PPF and aseptic stem loosening within the first postoperative year. Again, all research procedures are designed to align with standard perioperative and postoperative care for THA, minimizing burden for study participants. Additionally, the ACTIS Hip Stem (DePuy Synthes, Warsaw, IN) is routinely used by the participating surgeons for the last 3-4 years. The following outlines the specific protocol steps and time points:

Preoperative (Day -30 to 0):

- Obtain written informed consent either in person or via Interlace.
- Confirm eligibility criteria (inclusion/exclusion).
- Record baseline demographic data, diagnosis, and Dorr classification (from preop imaging).
- Randomization and group assignment.

Operative Day (Day 0):

- THA performed using the allocated femoral stem type (collared or collarless), via a standard surgical approach.
- Per standard practice, intraoperative documentation of any complications, including intraoperative PPFs, will be recorded by the surgical team.

Postoperative Follow-Up:

- Routine anterior-posterior (AP) pelvic and lateral hip X-rays will be obtained at 6 weeks, 6 months, and 1 year.

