- Subsidence will be quantified using standardized radiographic measurement techniques. Typically, radiographs are obtained at 6 weeks, 6 months and annually thereafter. Calibration will be performed with the known femoral head size and subsidence measured by standard techniques on these serial radiographs.

Adverse Event Monitoring (Ongoing):

- Any PPFs or aseptic loosening will be identified through clinical assessment, imaging review, and/or surgical reports, and reported by trained investigators or study staff.
- Participants will be advised to report any fall or unusual hip symptoms. Any clinically indicated imaging or intervention will be reviewed for endpoint classification.

Risk Minimization:

- All surgeries will be conducted by experienced orthopaedic surgeons within the MedStar Health System (MedStar Georgetown University Hospital and MedStar Washington Hospital Center) to minimize procedural variability.

MOD00024127

Page 7 of 18

Revised: November 12, 2025 IRB Approved

12/18/2025 - 11/3/2026

PROTOCOL TITLE: Comparison of clinical and radiographic results of collared and collarless femoral stems in total hip arthroplasty

- Standard sterile technique and perioperative protocols will be followed.
- Follow-up visits coincide with routine care to minimize patient burden.
- Radiographic measurements will be conducted by independent reviewers to reduce measurement error and bias.
- There is no additional physical risk to participating in this study beyond standard of care.
- The primary risk is a potential breach of confidentiality. To minimize this risk, all data will be de-identified and stored on password-protected, HIPAA-compliant platforms. Participants will be assigned a unique study ID (SID), and any linkage to identifiable information (e.g., MRN) will be stored separately in a secured, password-protected file. No patient names or identifiers will be recorded on any data collection forms.
- Study participants will be made aware about the risk of randomization for the implant they will receive. By participating in the study, the surgeons will not be able to choose the implant.

Devices Used:

- Collared and collarless femoral stems, both commercially available and FDA cleared for primary THA use—the ACTIS Hip Stem that comes in both a collared and collarless variation, will be used.
- Both stem types are used in current clinical practice and do not represent investigational use.

Source Records:

- Source documentation will include:

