 - Electronic medical records (EMR)
 - Operative reports
 - Imaging records (X-rays)
 - Clinic visit notes
- Patient-reported outcome forms—collected in OBERD, the standard platform at MedStar for collecting PROMs

Data Collected:

- Demographics and clinical variables: age, sex, BMI, comorbidities, Dorr classification.
- Operative data: stem type, surgical approach, intraoperative complications.
- Primary endpoint: femoral stem subsidence at 6 weeks, 6 months, and 1 year, measured in millimeters from standardized serial radiographs.
- Secondary endpoints:
 - PPF incidence (confirmed radiographically or operatively).
 - Aseptic loosening (evidenced by radiolucent lines, implant migration, or revision surgery).
- Other outcomes: functional scores (PROMs), adverse events, and reoperation rates.

MOD00024127

Page 8 of 18

Revised: November 12, 2025 IRB Approved

12/18/2025 - 11/3/2026

PROTOCOL TITLE: Comparison of clinical and radiographic results of collared and collarless femoral stems in total hip arthroplasty

Data Collection Methods:

- Radiographic analysis performed by independent reviewers blinded to group allocation.
- Adverse events recorded by research staff at each visit and during any interim visits.

Long-Term Follow-Up — Patients will follow standard protocol for follow-up, offering the possibility of more longitudinal reporting potentially 5-10 years postop.

Humanitarian Use Device (HUD) — N/A

This study does not involve any HUDs. All devices used (collared and collarless femoral stems) are FDA-approved for standard use in primary THA and do not require an Investigational Device Exemption (IDE). The 510(k) number for the collared hip stem is K150862 and for the collarless version is K21058.

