10.0 Inclusion and Exclusion Criteria*

Potential participants will be identified from the MedStar Orthopaedic Surgery clinics at MGUH and MWHC. Screening will occur during routine preoperative consultation visits for patients scheduled to undergo primary, uncemented THA due to osteoarthritis or other non-inflammatory degenerative joint disease.

Patients will be screened by the study investigator or trained research coordinator. Screening will involve review of the EMR for clinical and radiographic eligibility,

MOD00024127

Page 9 of 18

Revised: November 12, 2025 IRB Approved

12/18/2025 - 11/3/2026

PROTOCOL TITLE: Comparison of clinical and radiographic results of collared and collarless femoral stems in total hip arthroplasty

verification of surgical plan, preoperative radiographic assessment, and assessment of patient capacity to provide informed consent. Patients who meet all inclusion criteria and none of the exclusion criteria will be approached for informed consent and formally enrolled after confirming eligibility.

Inclusion Criteria:

- Adults (≥ 18 years old) scheduled for primary, uncemented THA using a cementless femoral stem.
- Diagnosis of primary osteoarthritis or other non-inflammatory degenerative joint disease.
- Ability and willingness to comply with study procedures and follow-up schedule.
- Ability to provide written informed consent.

Exclusion Criteria:

PROTOCOL TITLE: Comparison of clinical and radiographic results of collared and collarless femoral stems in total hip arthroplasty

- **Patients not indicated for a cementless THA.**
 - Prior surgery on the ipsilateral hip (e.g., prior THA, internal fixation, osteotomy).
 - Use of cemented or hybrid femoral components.
 - Revision THA or conversion THA.
 - Active or prior infection of the hip joint.
 - Severe osteoporosis (T-score ≤ -2.5) or known metabolic bone disease.
 - Inability to complete follow-up or anticipated relocation out of the area.

Special Populations:

The following special populations will be excluded from participation in this study: adults unable to provide consent, anyone under the age of 18, and pregnant women.

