14.0 Withdrawal of Subjects*

A subject may choose to withdraw from the study at any time. Withdrawal of a subject will have no effect on their clinical care or clinical decision making.

Subjects may also be withdrawn from the study without their consent under the following circumstances:

- Intraoperative change in surgical plan, such as conversion to a cemented or hybrid femoral stem, revision THA, or significant intraoperative complications rendering the assigned study implant unusable.
- Failure to attend postoperative follow-up appointments necessary for primary or secondary outcome data collection.
- Medical conditions or complications (e.g., infection, stroke, malignancy) that significantly impact the participant's ability to safely continue study participation or follow the protocol.
- Protocol violation identified by the research team that invalidates study participation (e.g., unintentional enrollment of an ineligible subject).

In all such cases, the reason for withdrawal will be documented in the subject's research file and medical record.

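### Section 14.0 allows withdrawal for ineligibility found at any time after randomization, so withdrawal can depend on outcome; the unmeasured T-score exclusion gives it a route

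*Protocol*

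**What the plan says.** Protocol Section 14.0 lists circumstances in which a subject may be withdrawn without consent. The fourth is a "Protocol violation identified by the research team that invalidates study participation (e.g., unintentional enrollment of an ineligible subject"). On what follows, the section says only: "In all such cases, the reason for withdrawal will be documented in the subject's research file and medical record". It does not mention further follow-up or the fate of outcomes already recorded.

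Section 10.0 excludes "Severe osteoporosis (T-score ≤ -2.5) or known metabolic bone disease". As written, the word 'known' attaches to metabolic bone disease and not to the T-score. The same section describes screening: "Screening will involve review of the EMR for clinical and radiographic eligibility", followed by "verification of surgical plan, preoperative radiographic assessment, and assessment of patient capacity to provide informed consent". No bone-density measurement is listed. Section 6.0 places the step "Confirm eligibility criteria (inclusion/exclusion") before surgery.

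Fracture is a secondary endpoint, recorded in Section 6.0 as "PPF incidence (confirmed radiographically or operatively"). On detection, that section says: "Any PPFs or aseptic loosening will be identified through clinical assessment, imaging review, and/or surgical reports, and reported by trained investigators or study staff". Blinding is stated there for the radiographic readers only.

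**The concern.** Removing patients for ineligibility after randomization is harmless only if the reason was fixed before allocation and could be found equally in every patient. Neither condition is written here.

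The T-score criterion shows how this could go wrong. A patient with low bone density and no value on file passes the listed screening. If that patient fractures, the team has a reason to look at bone quality; if not, there is no such prompt. The first patient can then be declared ineligible and withdrawn, while an otherwise identical patient without a fracture stays in. Those deciding are not said to be unaware of the stem used, and the surgeons who implant it know which it was.

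At stake are the completeness of fracture reporting under aim SA3 and the later subsidence readings, which belong to the primary endpoint. Section 3.0 justifies the trial partly by the failure of earlier work to capture intraoperative fractures, so a rule that does not protect fracture cases works against the trial's stated purpose.

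**Working it through.** **1. The plan's own figure.** Inputs from Section 17.0: difference 0.4 mm, SD 0.45 mm, alpha 0.05 (two-sided assumed), power 80%.

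n per group = 2 × (1.960 + 0.842)² × 0.45² / 0.4² = 2 × 7.85 × 0.2025 / 0.16 ≈ 19.9, so 20.

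This reproduces the stated 20 per group. The normal approximation gives 80.3% power at 20; the exact t calculation gives 78.2% at 20 and 80.3% at 21. The present point does not change this figure.

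**2. The provisions side by side.**

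| Question | What the protocol provides |
|---|---|
| When may ineligibility be found? | No limit (14.0) |
| On what information? | Not restricted to facts before randomization (14.0) |
| By whom? | The research team; blinding to arm or outcome not required (14.0) |
| Is the T-score measured at screening? | Not listed; record review would catch a value on file (10.0) |
| What is kept after withdrawal? | The reason is documented; nothing is said on events or visits (14.0) |

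**3. Primary-endpoint data at risk.** Subsidence is read at 6 weeks, 6 months and 1 year (Section 4.0). For a patient who fractures at month 3 (illustration) and is then withdrawn, two of the three readings lie ahead. The visits are routine care and may well take place, but the protocol does not provide for using them as study data after withdrawal.

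**4. Expected fractures.** Section 3.0 cites 90-day rates of 0.4% with a collar and 1.6% without. With 50 per group (Section 12.0):

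- Collared: 50 × 0.004 = 0.2
- Collarless: 50 × 0.016 = 0.8
- Total: 1.0
- Chance of at least one: 1 − 0.996^50 × 0.984^50 = 63.5%

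**5. If a share f of fracture cases were lost.** The protocol gives no value for f, so these are assumed. The small change in denominators is ignored.

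| f | Expected cases lost if f applies to both arms | Rate ratio, same f in both arms | Risk difference, same f in both arms | Rate ratio, collarless arm only |
|---|---|---|---|---|
| 0 | 0 | 4.0 | 1.20 points | 4.0 |
| 10% | 0.10 | 4.0 | 1.08 points | 3.6 |
| 25% | 0.25 | 4.0 | 0.90 points | 3.0 |
| 50% | 0.50 | 4.0 | 0.60 points | 2.0 |

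The rate ratio moves only if removal differs by arm. With equal removal, the incidences and their difference shrink in proportion.

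**6. Power for fracture.** At the cited rates about 1,079 per group would be needed for 80% power. At 50 per group, Fisher's exact test has about 0.01% power. The harm is therefore to the reported incidence, not to a significance test.

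**The case against.** The strongest reply is that withdrawal is not deletion. A reader might infer that the fracture endpoint erases its own cases, but the documents do not support that. A fracture that prompts the discovery comes before the withdrawal and would already have been recorded under Section 6.0. Whether it counts depends on the analysis set, which may be defined in a statistical analysis plan not shown. This part of the objection stands.

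Three further points carry weight:

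- No section provides for bone-density testing after a fracture. That step is a plausible inference, not a stated procedure.
- The natural reading of the bullet is a screening error, such as a T-score on file that was missed. A patient screened exactly as prescribed was arguably enrolled without any violation, and a value measured months later is not a baseline value. The wording of the criterion leaves this open, because it does not limit the T-score to known values.
- A reader might infer that removals would hide the collar's effect. At equal removal in both arms the ratio stays at 4.0, and attenuation requires removal that differs by arm. Nor would all of the one expected fracture be lost: at an assumed 5–25%, 0.05 to 0.25 cases would go.

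The first bullet of Section 14.0, on intraoperative complications that make the assigned stem unusable, is also a more direct route for losing fracture cases. It is a separate matter, and correcting it would leave this route open.

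The objection does not dispose of the withdrawal rule itself, which is protocol content. An analysis plan can decide how to treat recorded events, but it cannot recover visits that were never collected.

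**Conclusion.** The point holds in a limited form. Section 14.0 permits withdrawal after randomization for ineligibility found at any time, on any information, by people not required to be blind to arm or outcome. Together with a T-score exclusion that screening does not measure, this allows withdrawal to depend on outcome. It puts later subsidence readings at risk and leaves fracture cases unprotected.

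The likely size is small in absolute terms. About 1.0 fracture is expected in 100 patients, and only some fraction of that could be affected. That total rests on 90-day rates from a cited cohort; the trial follows patients for 1 year and also counts intraoperative fractures, so the true number may differ. With so few events, one case handled differently can change the reported incidence materially. The direction and size of any bias in the arm comparison cannot be fixed from the documents. The sample size for subsidence is unaffected. The wording should be changed, but this does not undermine the trial as a whole.

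**What to change.** Replace the fourth bullet of Section 14.0 with a rule that patients found ineligible after randomization stay in follow-up and are analysed in their allocated group, with all recorded events kept and the violation documented.

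If any exclusion for ineligibility is retained, limit it to information documented before randomization, judged by someone unaware of allocation and outcome.

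In Section 10.0, state that the T-score criterion is judged on values on record before randomization. This makes the criterion match the screening already described and adds no test.

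The cost is protocol wording only, with no extra patients or visits beyond those planned. The downside is that a few technically ineligible patients remain in the main comparison; a sensitivity analysis without them can address that.

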15.0 Risks to Subjects*

Since this study aligns with standard of care for THA procedures, and no investigational devices or additional interventions are introduced beyond routine care, participation in the research carries minimal risk. However, the following potential risks and inconveniences apply:

Physical Risks:

- Radiation exposure from X-rays: Although all imaging is part of routine clinical follow-up and not performed solely for research purposes, participants will

MOD00024127

Page 12 of 18 Revised: November 12, 2025 IRB Approved

12/18/2025 - 11/3/2026

PROTOCOL TITLE: Comparison of clinical and radiographic results of collared and collarless femoral stems in total hip arthroplasty

- undergo three radiographic evaluations (6 weeks, 6 months, and 1 year). The radiation dose is low and well within accepted clinical safety standards.
- Standard surgical risks: These include pain, infection, dislocation, periprosthetic fracture, implant loosening, nerve or vascular injury, and deep vein thrombosis (DVT). However, these risks are inherent to any THA procedure and are not elevated by study participation.
- Increased awareness of complications: Participation may involve increased attention to postoperative outcomes, which could potentially lead to increased anxiety regarding complications.
- Risk of randomization: This study removes the elements of choice from the practicing surgeon. Currently, there is no definitive data based on prospective studies that suggests that one is better than the other. While improvement of symptoms is expected for both implants for all patients, there may be general differences in the clinical and radiographic results between the two.

Psychological and Social Risks:

- There are no direct psychological risks anticipated, but some participants may experience mild anxiety related to study participation, data monitoring, or followup imaging results.
- Privacy risks are minimal due to the use of secure, HIPAA-compliant data systems and appropriate de-identification of research data.

16.0 Potential Benefits to Subjects*

There is no guaranteed direct benefit to participants for taking part in this research study. The primary goal of this study is to generate knowledge that may improve care for future patients undergoing THA. While this research study is designed primarily to gather knowledge on the comparative outcomes of collared versus collarless femoral stems in total hip arthroplasty (THA), there may be limited, indirect benefits to individual participants. These potential benefits include:

- Increased clinical oversight: Study participants may experience enhanced monitoring through standardized radiographic follow-up and evaluation by trained research staff, which could aid in early identification of implant-related complications.
- Educational benefit: Participants may gain a greater understanding of their surgical procedure and postoperative course through discussions with the study team.

MOD00024127

Page 13 of 18 Revised: November 12, 2025 IRB Approved

12/18/2025 - 11/3/2026

PROTOCOL TITLE: Comparison of clinical and radiographic results of collared and collarless femoral stems in total hip arthroplasty

17.0 Data Management* and Confidentiality

Femoral stem subsidence will be the primary outcome, measured in millimeters at 6 weeks, 6 months, and 1 year postoperatively. Differences in mean subsidence between the collared and collarless groups will be assessed using independent samples t-tests or nonparametric alternatives if assumptions of normality are not met. Incidence of PPF and aseptic loosening will be compared using chi-square tests or Fisher's exact tests. Logistic regression or Cox proportional hazards modeling will be used to adjust for covariates such as age, BMI, Dorr classification, and surgical approach if sample size allows. A sample size of 20 participants per group (40 total) provides 80% power to detect a difference of 0.4 mm in mean stem subsidence, assuming a standard deviation of 0.45 mm (based on prior RSA-based studies), with $\alpha = 0.05$. A proposed target enrollment of 100 participants is set to account for unforeseen dropouts.

All study team members will be trained in HIPAA compliance and Good Clinical Practice (GCP). Electronic data will be stored in a secure, password-protected, encrypted research database hosted on institutional servers. Subject identifiers (e.g., name, MRN) will be stored separately from study data and linked only via a unique coded identifier. Transmission of data between team members or collaborators will occur via encrypted institutional email or secure file-sharing platforms. No data will be shared externally without IRB and institutional approval.

Information Included:

- Demographic data, medical history, surgical details, implant type, radiographic images and measurements, and clinical outcomes (e.g., fracture, loosening, revision surgery).

Storage Location and Method:

- Data will be stored on secure, password-protected, encrypted institutional servers.
- Only authorized members of the research team listed on the IRB application will have access.
- The PI will oversee access and approve any data sharing requests.

18.0 Provisions to Monitor the Data to Ensure the Safety of Subjects – N/A

This proposed research study does not involve more than minimal risk to subjects, since it aligns with standard of care for THA procedures.

MOD00024127

Page 14 of 18 Revised: November 12, 2025 IRB Approved

12/18/2025 - 11/3/2026

PROTOCOL TITLE: Comparison of clinical and radiographic results of collared and collarless femoral stems in total hip arthroplasty

-

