11.0 Vulnerable Populations* - N/A

12.0 Local Number of Subjects

For this study we aim to enroll 100 participants (50 per group) undergoing primary, cementless THA across two MedStar sites, MedStar Georgetown University Hospital and MedStar Washington Hospital Center. All participants will be screened at the time of surgical scheduling and enrolled if they meet the criteria and consent to participate. This target number of 100 participants accounts for any dropouts throughout the study. Based on our power calculation (assuming 80% power, significance of 0.05, and a SD of 0.45 mm based on prior studies), a sample size of at least 20 subjects per group (40 in total) would be needed to complete the research procedures.

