13.0 Recruitment Methods

Recruitment will occur during standard preoperative clinic visits at the Department of Orthopedic Surgery at MGUH and MWHC. Potential subjects will be identified weekly by IRB-approved research staff by screening clinic appointments. Patients scheduled for primary, uncemented THA will be approached during these visits. Recruitment will begin after IRB approval and continue until the target enrollment of 100 participants is reached. Each potential participant will be approached in-person by a study investigator or trained research coordinator prior to surgery, typically 2–4 weeks in advance.

The study will be described in detail, and eligible patients will be provided with a written informed consent form and ample time to ask questions. If interested, they may sign the consent form at that time or take it home and return it during a subsequent visit. Patients may also choose to complete an electronic consent form

MOD00024127

Page 11 of 18 Revised: November 12, 2025 IRB Approved

12/18/2025 - 11/3/2026

PROTOCOL TITLE: Comparison of clinical and radiographic results of collared and collarless femoral stems in total hip arthroplasty

that can be sent to their emails through a secure MedStar consenting platform, Interlace.

All subjects will be under the routine clinical care of orthopaedic providers at the study institution and will be recruited without deviation from the standard clinical pathway for surgical planning and follow-up. Recruitment will occur entirely through face-to-face interaction during clinic visits, with no use of public advertisements, social media, or media broadcast. No posters or flyers regarding the study will be distributed.

No monetary compensation will be provided to participants for their involvement in this study.

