26.0 Resources Available

We anticipate screening approximately 100 patients in order to enroll at least 50 participants in adherence to our power calculation. MGUH and MWHC sees an ample number of patients for THA that should allow us to reach our target number within the stated timeframe (approximately 1 year). The total allotted timeframe we are devoting to conducting and completing this research is 2 years. Additional research members can be recruited as needed from the Georgetown School of Medicine and will be updated to the IRB.

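### The claim that 20 per group gives 80% power applies an RSA standard deviation to a plain-film endpoint with no margin, and Section 26 contradicts the enrolment target of 100

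*Protocol*

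**What the plan says.** **Sample size.** Section 17 gives 20 per group as providing 80% power for a 0.4 mm difference in mean subsidence at alpha 0.05, "assuming a standard deviation of 0.45 mm (based on prior RSA-based studies"). Section 12 repeats the result, "a sample size of at least 20 subjects per group (40 in total) would be needed", and describes the SD only as coming from earlier studies, without mentioning RSA. The surplus over 40 is explained in Section 17: "A proposed target enrollment of 100 participants is set to account for unforeseen dropouts". No dropout rate is given.

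**Measurement.** Section 6 specifies routine AP pelvic and lateral hip films at 6 weeks, 6 months and 1 year. On method it says "Calibration will be performed with the known femoral head size and subsidence measured by standard techniques on these serial radiographs", and its data list describes the primary endpoint as "measured in millimeters from standardized serial radiographs".

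**Enrolment.** Section 6 begins from "A total of 100 participants undergoing elective, uncemented primary THA". Section 13 says recruitment will "continue until the target enrollment of 100 participants is reached". Sections 1, 12 and 17 also give 100. Section 26 differs: "We anticipate screening approximately 100 patients in order to enroll at least 50 participants in adherence to our power calculation".

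**The concern.** The SD in a two-sample calculation is the total spread of the recorded values: true variation between patients plus the error of the measuring method. An SD taken from RSA carries RSA's measurement error, while this trial will carry the error of head-calibrated plain films. The protocol neither argues that the two are equal nor adds an allowance, so the power claim rests on an input from a different instrument.

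Two things follow. Read literally, Sections 12 and 17 would count a trial that ended with 20 completers per group as adequately powered, and a null result would be taken as evidence against a 0.4 mm difference. That reading needs plain films to be as precise as RSA. In addition, a reader of Section 26 cannot tell whether 50 or 100 patients fulfil the plan, or how many must be screened.

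**Working it through.** **Inputs.** From Sections 12 and 17: difference 0.4 mm, SD 0.45 mm, alpha 0.05, power 80%, independent-samples t-test (or a nonparametric alternative). From Sections 6 and 12: 1:1 allocation, 50 per group planned. Sidedness is not stated. The two-sided calculation reproduces the protocol's figure; a one-sided one would need 16.

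**Step 1: reproduce the stated figure.** Normal approximation, per group:

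n = 2 × (1.960 + 0.842)² × 0.45² / 0.4² = 19.87, so 20.

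The sum is correct by this method. With the t-test the protocol names (noncentral t), power is 78.2% at 20 per group and 80.3% at 21.

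**Step 2: how large an SD can each group size bear?** The limit is 0.4 mm divided by the standardised difference detectable with 80% power (two-sided t-test, alpha 0.05).

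| Analysed per group | Largest SD for 80% power at 0.4 mm |
|---|---|
| 20 (Sections 12, 17) | 0.44 mm |
| 25 (Section 26, if 50 is the total) | 0.49 mm |
| 40 (illustration: 20% dropout from 50) | 0.63 mm |
| 45 (illustration: 10% dropout from 50) | 0.67 mm |
| 50 (target) | 0.71 mm |

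**Step 3: power for 0.4 mm over a range of SDs.** The protocol gives no plain-film SD. The values from 0.6 to 1.0 mm are assumptions chosen to show sensitivity.

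| SD (mm) | Power, 20 per group | Power, 25 per group | Power, 50 per group | Needed per group for 80% |
|---|---|---|---|---|
| 0.45 (protocol) | 78% | 87% | 99% | 21 |
| 0.6 | 54% | 64% | 91% | 37 |
| 0.7 | 42% | 51% | 81% | 50 |
| 1.0 | 23% | 28% | 51% | 100 |

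The difference detectable with 80% power at 50 per group is 0.25, 0.34, 0.40 and 0.57 mm for these four SDs. At 20 per group it is 0.41, 0.55, 0.64 and 0.91 mm.

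**Step 4: what the dropout explanation implies.** Going from 100 enrolled to the 40 said to be needed is a loss of 1 − 40/100 = 60%. On the protocol's own terms, a trial that lost 60% of its patients would still have its stated power.

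**Step 5: the enrolment figures.**

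- Power calculation: 40 in total.
- Target in Sections 1, 6, 12, 13 and 17: 100.
- Section 26: at least 50, said to follow from the power calculation, out of about 100 screened.

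If 50 is a total, it equals neither 40 nor 100. If it means 50 per group, all of the roughly 100 screened would have to enrol, and the power calculation still says 20 per group. At Section 26's own yield of 50/100, enrolling 100 takes 100/0.5 = 200 screened.

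**The case against.** The strongest reply is that the trial as planned is not shown to be underpowered. The sum is right, and the gap between 80% and 78% is one patient per group, the difference between the normal approximation and the t-test. By the normal approximation the SD limit at 20 per group is 0.4 / [2.802 × √(2/20)] = 0.45 mm, so the protocol's own SD just passes. Recruitment runs to 50 per group, which gives 91% power at an SD of 0.6 mm and 81% at 0.7 mm, and with 20% dropout the limit is still 0.63 mm. Nothing in the protocol shows that the plain-film SD will exceed 0.71 mm. Section 6 also provides independent, blinded readers. On enrolment, at least 50 is a floor that 100 satisfies, it could be 40/(1 − 0.20) = 50, and Section 13 sets the stopping point at 100.

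Much of this stands. The absence of slack concerns the 20-per-group claim, not the planned 100, and the larger SDs are assumptions. But the protocol does not present the surplus as cover for measurement error: it assigns it to dropouts and calls 20 per group enough. Blinded independent reading limits bias and may reduce error, but it does not put plain-film error into the SD used. A floor of 50 still does not follow from a calculation that yields 40, the 20% explanation is nowhere in the text, and screening about 100 does not fit enrolling 100.

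**Conclusion.** The concern holds. The statement that 20 per group gives 80% power for 0.4 mm is unsupported for the endpoint this trial measures. By the planned t-test it fails at any SD above 0.44 mm, which is already just below the protocol's own 0.45 mm. The planned 50 per group is adequate up to an SD of 0.71 mm if all are analysed, and less after dropout; the protocol states neither that limit nor a dropout rate. Whether the real SD lies above or below the limit cannot be settled from the protocol, so this is an unsupported power claim and not a demonstrated shortfall. The calculation assumes a two-sided test and equal SDs in both groups. The Section 26 figure contradicts both the calculated 40 and the target of 100, and that point needs no assumption. The matter should be fixed, but it does not undermine the design.

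**What to change.** **Sections 12 and 17.** Remove the claim that 20 per group suffices. Base the power statement on the planned 100 less a dropout rate that the protocol states. Suggested wording:

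> The planning SD of 0.45 mm came from RSA studies; the SD on plain radiographs may be larger. With 50 analysed per group, a two-sided t-test at 0.05 has 80% power for 0.4 mm if the SD is at most 0.71 mm. For assumed plain-film SDs of 0.45, 0.6, 0.7 and 1.0 mm, the difference detectable with 80% power is 0.25, 0.34, 0.40 and 0.57 mm.

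These figures should then be recomputed for the completers expected after the stated dropout. If the sponsor has a sourced SD for head-calibrated plain films, it should replace the assumed range.

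**Section 26.** State 100 enrolled with a matching screening number. At that section's own yield this is about 200; because its 50 is a floor, fewer may be enough.

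**Cost.** Wording changes in three sections, with no extra patients, visits or films. The stated power becomes less favourable, and the protocol has to acknowledge that 100 patients do not give 80% power for 0.4 mm if the plain-film SD exceeds 0.71 mm.
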